## **6.3 Visit 1: 4 Weeks ( $\pm 1$ week) Follow-Up**

The following information will be collected:

- Device or Procedure-related adverse events
- Changes in indwelling urinary catheter use
- BPH related medications
- Additional prostate procedures and/or imaging
- Prostate specific antigen (PSA), if done

## **6.4 Visit 2, 3 & 4: 3 Months ( $\pm 2$ weeks), 12 Months ( $\pm 8$ weeks), 24 Months ( $\pm 8$ weeks) Follow-Up**

Study participation will last for a total of 24 months ( $\pm 8$  weeks). Traditional visit windows are being expanded to allow for potential impacts due to COVID-19.

The following information will be collected:

- International Prostate Symptom Score (IPSS)
  - Must be self-administered by patient
- Device or Procedure-related adverse events
- Changes in indwelling urinary catheter use
- BPH related medications
- Additional prostate procedures and/or imaging

- Urinary Evaluations (Qmax and PVR), if done
- Sexual Health Inventory for Men (SHIM), 12-months only
  - Must be self-administered by patient
- Prostate specific antigen (PSA), if done

If approved by the IRB/EC, patients may receive an honorarium for complying with follow-up data collection at 12 and 24 months.

## 6.5 Questionnaire Administration

The International Prostate Symptom Score (IPSS) and Sexual Health Inventory for Men (SHIM) are validated for self-administration by the patient. At baseline, the IPSS and SHIM will be self-administered by the patient preferably in person during an office visit. The applicable questionnaires may also be self-administered by the patient either in person, by mail, or by email at all follow-up visits.

## 6.6 Additional Evaluations

Data will also be collected for additional evaluations that occur at any times outside of the above protocol-defined timepoints. If a patient receives any additional PAE procedures with Embosphere Microspheres, he will remain in the study, and the schedule for the follow-up evaluations will begin according to the date of the first PAE with Embosphere Microspheres procedure until the subject reaches a total of 24 months follow-up. End of study at 24 months is calculated on subject's first PAE procedure and not any additional PAE procedures.

Table 1. Schedule of Events

Table 1 identifies the Schedule of Events below. Follow-up may occur in the form of an in-person office visit, phone call, or mail. Information may be collected by email or text if the patient has documented that this is acceptable.

	Baseline	PAE Procedure	Visit 1	Visit 2	Visit 3	Visit 4	Unscheduled Visits
			4 Weeks (±1 week/± 7 days)	3 Months (±2 weeks/± 14 days)	12 Months (±8 weeks/±56 days)	24 Months (±8 weeks/±56 days)	
Informed Consent	X						
Demographics	X						
Prostate Size Assessment	X 						
Prior BPH Procedures	X						
Prostate Biopsy	X 						X 
Prostate Specific Antigen (PSA)	X 		X		X		X 
PAE Procedure		X					
Sexual Health Inventory for Men (SHIM)	X 				X		
International Prostate Symptom Score (IPSS)	X 			X	X	X	X 

	Baseline	PAE Procedure	Visit 1	Visit 2	Visit 3	Visit 4	Unscheduled Visits
			4 Weeks (±1 week/± 7 days)	3 Months (±2 weeks/± 14 days)	12 Months (±8 weeks/±56 days)	24 Months (±8 weeks/±56 days)	
BPH related medications (5α-Reductase inhibitors, α-blockers, etc.)	X		X	X	X	X	X 
Device or Procedure-Related Adverse Events		X	X	X	X	X	X 
Urinary Evaluations (Indwelling urinary catheter use, Qmax and PVR)	X 			X	X	X	X 
Additional prostate procedures and/or imaging			X	X	X	X	X 

 Prostate biopsy within 12 months of PAE procedure

 Baseline SHIM to occur within 4 weeks of PAE procedure

 Baseline IPSS to occur within 4 weeks of PAE procedure

 Within timeframe consistent with standard of care

 Unscheduled visits may include one or more of the identified evaluations

## 7 Patient Completion and Discontinuation

Patients will be informed that they have the right to withdraw from the study at any time for any reason, without prejudice to their medical care. The investigator also has the right to withdraw patients from the study for any reason. If a patient is withdrawn or discontinued from the study, the reason for withdrawal from the study will be recorded on the end of study form. These subjects will not be replaced.

A subject will be considered lost to follow-up if he fails to return for more than one scheduled visit and is unable to be contacted by the study site staff.

The following actions must be taken if a subject fails to return for a required study visit:

- The site will attempt to contact the subject and reschedule the missed visit within the allowable visit timeline and counsel the subject on the importance of maintaining the assigned visit schedule and ascertain if the subject wishes to and/or should continue in the study
- Before a subject is deemed lost to follow-up, the Investigator(s) or designees will make every effort to regain contact with the subject (where possible, 3 telephone calls and, if necessary, a certified letter to the subject's last known mailing address or local equivalent methods). These contact attempts must be documented

- Should the subject continue to be unreachable, he or she will be considered to have withdrawn from the study with a primary reason of lost to follow-up

If a patient receives any non-PAE BPH procedure other than biopsy after his study PAE he will be automatically discontinued from the study, and follow-up data will no longer be collected. BPH procedures that will automatically discontinue the patient include but are not limited to TURP, Urolift, microwave ablation, aquablation, laser therapy and non-Embosphere Microspheres PAE.

Patients requiring multiple PAE procedures:

- If a patient receives an additional PAE procedure with Embosphere Microspheres after the initial treatment, he will remain in the study, and the schedule for the follow-up evaluations will begin according to the date of the first PAE with Embosphere Microspheres procedure until the subject reaches a total of 24 months follow-up. End of study will be calculated based on first PAE procedure for 24 months.
- If a patient receives more than one PAE procedure to complete the initial treatment, he will remain in the study, and the schedule of the follow-up evaluations will begin according to the date of the first PAE with Embosphere Microspheres, but not to exceed a total of 24 months from initial treatment date.

## **8 Statistical Considerations**

### **8.1 Endpoint Definitions**

#### **8.1.1 Primary Endpoints**

The primary endpoint is the IPSS at 12 months.

#### **8.1.2 Secondary Endpoints**

The following are the secondary endpoints:

- IPSS measured at 3, 12, and 24 months post-baseline
- Device or Procedure-Related Adverse event rate at post-procedure, 3, 12, and 24 months
- Technical Success defined as the successful embolization of the treated prostate gland
- Frequency of indwelling bladder catheter removal post PAE at 3, 12, and 24 months
- Number of patients and types of treatment for refractory or recurrent LUTS due to BPH post PAE at 3, 12, and 24 months
- Change from baseline in Sexual Health Inventory for Men (SHIM) at 12 months post-PAE.

#### **8.1.3 Exploratory Endpoints**

During unscheduled visits, depending on the site's standard of care, the following measurement may be collected during the visit:

- Maximum Urinary Flow Rate (Qmax)

- Pulse Volume Recording
- Prostate-Specific Antigen
- Prostate size assessment
- Prostate biopsy

## 8.2 Primary Statistical Objective

The primary statistical objective is to evaluate the efficacy of the device by estimating the change from baseline in the 12 month IPSS within +/- 1 unit.

## 8.3 Sample Size

The sample size is based on the following assumptions

- Four countries with asymmetrical countrywide enrollments ranging from 15% to 25% of the total enrollment (conservative assumption)
- Standard Deviation = 8.5
- Difference between the lower and upper 2-sided 95% Confidence interval = 2
- 10% of patients missing either baseline or 12 month IPSS

A sample size of up to 500 patients is required to estimate the 12 month change from baseline in the IPSS within +/- 1 unit. Sample size calculations were performed using NCSS PASS 2020's procedure for one mean in a stratified design.

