Embolization of prostate arteries has been used for many years to control serious bleeding after biopsy or prostatectomy. The first published case in which it was recognized that embolization could have a therapeutic effect on benign prostatic hyperplasia (BPH) was by DeMeritt and colleagues. Prostate artery embolization (PAE) is an emerging therapy for LUTS associated with BPH, and has been demonstrated to reduce symptom burden, improve urodynamic measures, and decrease prostate size. On April 16, 2013 Embosphere Microspheres received the CE mark for the indication of embolization of the prostate gland for relief of symptoms related to benign prostatic hyperplasia, and on June 21, 2017 Merit Medical Systems, Inc received 513(f)(2) (de novo) classification from the FDA to expand the indication for Embosphere Microspheres to include prostatic artery embolization (PAE) for symptomatic benign prostatic hyperplasia (BPH).

The indication was granted based on the outcomes of published and unpublished data from 286 patients. The cohort is typical of the patient population treated for symptomatic benign prostatic hyperplasia. Mean age at baseline was  $67.7 \pm 9.7$ , lower urinary tract symptoms were severe as reflected in a mean International Prostate Symptom Score (IPSS) of  $21.5 \pm 6.8$ , and mean quality of life (QOL) score from the IPSS questionnaire was  $4.8 \pm 0.9$  ("mostly dissatisfied" to "unhappy"). Bilateral prostate embolization was achieved in 254 patients (88.9%), despite including 32 patients over the age of 80 and 54 with indwelling catheters at baseline for management of acute urinary retention. Mean symptom scores improved significantly compared to pretreatment values at every follow up interval. Mean IPSS scores improved from  $21.5 \pm 6.8$  at baseline to  $6.3 \pm 5.8$  ( $<0.0001$ ) and  $6.2 \pm 5.8$  ( $<0.0001$ ) at the 1-

3 month and 9-16-month follow-ups respectively. A reduction of IPSS score by at least 3 points was achieved at 9-16 months in 97% of patients, and 90% dropped by at least 1 symptom category.

The reduction of LUTS reflected in the IPSS changes affected mean quality of life. Mean QOL scores improved significantly from  $4.8 \pm 0.9$  ("mostly dissatisfied" to "unhappy") pre-embolization to  $1.4 \pm 1.2$  ( $<0.0001$ ) and  $1.4 \pm 1.1$  ( $<0.0001$ ; "pleased"/ "mostly satisfied") at the 1-3 month and 9-16-month follow-ups respectively.

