## 4 Study Design

This is a prospective, open label post market study to evaluate the long-term safety and effectiveness of PAE using Embosphere Microspheres. Up to 500 patients with LUTS due to BPH will be enrolled in this single arm post market study. All patients at sites who meet eligibility criteria will be offered participation. Long term effectiveness of PAE on LUTS will be evaluated by IPSS score at baseline, 3 months, 12 months, and 24 months. Note: All subjects will be asked to complete the IPSS. However, study subjects who have an indwelling bladder catheter will not be required to complete the IPSS; the IPSS questions may not be relevant to subjects with an indwelling bladder catheter. Safety will be assessed by evaluating device and procedure-related adverse events at the same time points, plus at 4 weeks following embolization. Erectile function will be assessed at baseline and 12 months by SHIM score. Additional treatments for refractory or recurrent LUTS due to BPH post prostatic artery embolization will also be recorded.

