### 8.4.2 Evaluable Analysis Set (EAS)

Includes FAS patients where there are no significant deviations (e.g. not meeting the inclusion/exclusion criteria) from the protocol that did not have an indwelling catheter at the end of the procedure.

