## 8.5.2 Analysis of the Primary Endpoint

The stratified sample mean change from baseline in 12 month IPSS is estimated as follows.

$$\bar{x} = \sum_{h=1}^L \frac{N_h}{N} \sum_{i=1}^{n_h} \frac{X_{hi}}{n_h} = \sum_{h=1}^L \frac{N_h}{N} \bar{x}_h$$

where  $\bar{x}$  is the stratified sample mean,  $L$  is the number of strata,  $X_{hi}$  is change from baseline in 12 month IPSS for the  $i^{th}$  patient in the  $h^{th}$  stratum,  $N$  is the overall sample size and  $N_h$  is the sample size in stratum  $h$

It can be shown in T. Yahane(1967) that the expected value and variance of  $\bar{x}$  ( $V(\bar{x})$ ) assuming sampling without replacement are

$$E(\bar{x}) = \mu$$

$$V(\bar{x}) = \sum_{h=1}^L \left(\frac{N_h}{N}\right)^2 \left(\frac{N_h - n_h}{N_h n_h}\right) S_h^2$$

$$S_h^2 = \frac{1}{N_h - 1} \sum_{i=1}^{N_h} (X_{hi} - \mu_h)^2$$

where

The 95% confidence interval ( $CI(\mu)$ )s calculated as follows:

$$CI(\mu) = \bar{x} \pm z_{1-\alpha/2} \sqrt{\hat{V}(\bar{x})}$$

where  $\alpha$  is the type I error and  $\hat{V}(\bar{x})$  is the unbiased estimator of  $V(\bar{x})$  and is calculated as follows:

$$\hat{V}(\bar{x}) = \sum_{h=1}^L \left(\frac{N_h}{N}\right)^2 \left(\frac{N_h - n_h}{N_h n_h}\right) S_h^2$$

$$s_h^2 = \frac{1}{n_h - 1} \sum_{i=1}^{n_h} (X_{hi} - \bar{x}_h)^2$$

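### Section 8.3 gives 500 patients as the size needed for ±1 IPSS unit, but its stated inputs give 309 to 312, and its four country shares cannot total 100%.

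*Combined protocol and SAP*

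**What the plan says.** The study is sized on precision, not power. Section 8.2 sets the primary statistical objective as estimating the 12-month change from baseline in IPSS to within 1 unit either way. Section 8.3 lists four assumptions:

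- country strata: "Four countries with asymmetrical countrywide enrollments ranging from 15% to 25% of the total enrollment (conservative assumption"
- a standard deviation of 8.5
- a two-sided 95% confidence interval with a total width of 2
- missing data: "10% of patients missing either baseline or 12 month IPSS"

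It concludes: "A sample size of up to 500 patients is required to estimate the 12 month change from baseline in the IPSS" at that precision, and names the PASS 2020 procedure for one mean in a stratified design. It gives no stratum sizes, stratum-specific SDs or allocation.

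Section 4 uses the same number as a ceiling: "Up to 500 patients with LUTS due to BPH will be enrolled in this single arm post market study". Section 8.5.2 gives the estimator ("The stratified sample mean change from baseline in 12 month IPSS is estimated as follows"). It weights each stratum mean by N_h/N, where N_h is defined as the stratum's own sample size.

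**The concern.** A reader who puts the section 8.3 inputs into the usual formula for the precision of a mean gets a number near 310, not 500. The one listed input that might explain the gap, the country stratification, is internally impossible as described. So the stated size and the stated precision do not come from the same visible calculation. Because ±1 unit is also the primary statistical objective, this is the only stated basis for the study's size. A reader cannot tell whether the SD, the missing-data rate or the strata is misreported, or whether an input was left out.

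**Working it through.** **Inputs (section 8.3).** SD = 8.5; two-sided 95% interval of total width 2, so half-width d = 1; 10% missing; four countries at 15% to 25% each.

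**1. Attempt to reproduce 500.**

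- Normal quantile: n = (z × SD / d)² = (1.95996 × 8.5 / 1)² = 277.5, so 278 evaluable. Enrolled: 278 / 0.9 = 308.9, so **309**.
- t quantile: the smallest n with t(0.975, n−1) × 8.5 / √n ≤ 1 is 280. Enrolled: 280 / 0.9 = 311.1, so **312**.

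The stated 500 is about 60% higher and is not reproduced.

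**2. Does stratification close the gap?** Under section 8.5.2, and leaving aside the finite-population factor, the variance is Σ (N_h/N)² × SD² / n_h. With a common SD and equal missingness, n_h/n = N_h/N, and the sum reduces to SD²/n. The inflation is 1.00. The finite-population factor can only lower the variance.

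**3. Do the shares add up?** Four shares capped at 25% total 100% only if all are exactly 25%, which is neither asymmetrical nor compatible with a 15% lower end. With one country at 15%, the maximum is 15 + 3 × 25 = 90%.

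**4. Worst case within the stated range.** Rescale shares of 15/15/25/25 to 100% (an assumption), giving 18.75/18.75/31.25/31.25%, and reverse the allocation against the weights:

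Σ w²/a = 2 × 0.1875²/0.3125 + 2 × 0.3125²/0.1875 = 0.225 + 1.042 = 1.267

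Then 277.5 × 1.267 ≈ 352 evaluable and about **391** enrolled.

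**5. What would give about 500?** Enrolling 500 with 10% missing leaves 450 evaluable. To need 450 requires one of the following, none of which is stated:

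- SD = √450 / 1.96 = 10.8
- variance inflation of 450 / 277.5 = 1.62
- 8.5 read as a single-visit SD with a baseline to 12-month correlation of 0.2: the SD of the change is 8.5 × √(2 × 0.8) = 10.75, giving 445 evaluable and 495 enrolled
- country weights outside the stated range, such as 15/20/25/40% with reversed allocation: Σ w²/a = 1.595, giving 443 evaluable and about 492 enrolled

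Two other common variants also miss. Requiring 80% to 99% assurance on the interval width gives 333 to 370 enrolled. A 98% interval gives 436 and a 99% interval gives 534.

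**6. Precision at 500.** 1.96 × 8.5 / √450 = **0.785**. The ±1 target holds while at least 278 / 500 = 55.6% are evaluable, so up to about 44% may be lost.

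**The case against.** The strongest reply is that the wording is a ceiling, that ±0.79 lies within ±1, and that the PASS run has not been seen. On that view the section is unreproducible rather than wrong. Also, labelling the country split conservative suggests that stratification was meant to raise the size, while 309 to 312 assumes proportional allocation and a common SD.

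A figure near 500 can be approached by stacking allowances. Take the worst-case 352 evaluable and add a separate catheter loss. Section 4 says "study subjects who have an indwelling bladder catheter will not be required to complete the IPSS", section 8.4.2 limits the EAS to patients who "did not have an indwelling catheter at the end of the procedure", and the 286-patient cohort in section 1 included "54 with indwelling catheters at baseline for management of acute urinary retention". With 54/286 = 18.9% lost in addition to the 10%, 352 / (0.9 × 0.811) ≈ 482.

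Part of this stands. 500 meets the objective, the error is in the conservative direction, and a hidden input could explain the number. The rest does not:

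- Section 8.3 presents the figure as the size needed for ±1, not only as a cap.
- No combination of the inputs it lists gives 500. Unfavourable allocation within the stated range stops at about 391.
- The route to 482 adds a catheter loss that section 8.3 does not state to a deliberately worst-case mismatch. The catheter loss without that mismatch gives 278 / 0.811 ≈ 343 if it overlaps fully with the 10%, or 278 / (0.811 × 0.9) ≈ 381 if separate.
- The share problem needs no modelling assumption.

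**Conclusion.** The concern holds, and the sample size justification is wrong as written. The stated inputs call for 309 enrolled (312 with t), against a stated 500. The country shares cannot total 100% unless all four are equal, which the text rules out.

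The 309 to 312 figure assumes a common SD of 8.5 for the change score, equal missingness across countries, and allocation in line with the section 8.5.2 weights. Relaxing the last within the rescaled shares raises it to about 391 at most.

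The consequence is limited. At 500 enrolled the half-width is about 0.79 with 10% missing. It would be 0.83 to 0.87 if 18.9% were non-evaluable because of catheters (an assumption borrowed from the cited cohort; 406 or 365 evaluable). The study is not undersized, and no conclusion depends on the discrepancy.

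**What to change.** Reword section 8.3:

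1. Give four country shares that total 100%, and the PASS inputs used: stratum sizes, stratum SDs and allocation.
2. Either state 309 to 312 enrolled (278 to 280 evaluable) as the size needed for ±1 and describe 500 as an enrolment cap with expected precision of about ±0.79, or state the additional input that yields 500.
3. As a clarification, say whether the 10% allowance includes catheterised patients without an IPSS. If it does not, give the assumed non-evaluable share.

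The cost is the rewording of one section. Enrolment does not need to change.

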## 8.4 Analysis Populations

### 8.4.1 Full Analysis Set (FAS)

Includes all patients that were enrolled except those that withdrew consent before the index procedure. The FAS is the population that will be used in determining endpoints except for efficacy endpoints

### 8.4.2 Evaluable Analysis Set (EAS)

Includes FAS patients where there are no significant deviations (e.g. not meeting the inclusion/exclusion criteria) from the protocol that did not have an indwelling catheter at the end of the procedure.

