## **2 Study Rationale**

Prostatic artery embolization with Embosphere Microspheres is a relatively new procedure. The goal of this post market study is to evaluate long-term safety and effectiveness in a 'real world' setting.

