## 5 Eligibility Criteria

- Inclusion Criteria
  - Patient has signed informed consent
  - Patient age is 18 years or older at time of informed consent
  - Patient will undergo PAE with Embosphere Microspheres for the treatment of symptomatic BPH with LUTS
- Exclusion Criteria
  - Patient is unable or unwilling to provide follow-up information
  - Patient is undergoing PAE for reasons that do not include symptomatic BPH with LUTS
  - Any other reason the investigator deems cause for exclusion

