## **15 Subject Enrollment**

All patients requiring an intervention due to reasons detailed in this protocol are potential study candidates and shall be screened for eligibility. Subjects who are consented and meet all the study inclusion criteria and none of the study exclusion criteria and are treated or attempted to be treated will be considered enrolled into the study.

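### The primary IPSS result appears to rest only on a set that drops treated men for undefined significant deviations, with no lock on the exclusions and no all-treated analysis

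*Combined protocol and SAP*

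**What the plan says.** Section 8.4.1 builds the FAS from enrolled men and limits its use: "The FAS is the population that will be used in determining endpoints except for efficacy endpoints". Section 8.4.2 then defines the EAS: "Includes FAS patients where there are no significant deviations (e.g. not meeting the inclusion/exclusion criteria) from the protocol". A second condition restricts it to men "that did not have an indwelling catheter at the end of the procedure"; that catheter condition is a separate matter. Eligibility failure is the only example given of a significant deviation, and it is introduced as an example, not as a list.

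Section 5 has three exclusion criteria, one of which is "Any other reason the investigator deems cause for exclusion". Section 15 says that men who "meet all the study inclusion criteria and none of the study exclusion criteria and are treated or attempted to be treated will be considered enrolled".

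Section 8.5.2 gives the estimator for the 12-month IPSS change but names no population. Its sensitivity work, in 8.5.2.1, concerns missing data only. Sections 8.5.3.1 (IPSS over time) and 8.5.3.6 (SHIM) name the EAS. Section 8.5.1.7 says that secondary endpoints use the FAS.

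On design, section 4 states: "This is a prospective, open label post market study". On purpose, section 2 states: "The goal of this post market study is to evaluate long-term safety and effectiveness in a" real-world setting.

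**The concern.** A set that drops treated men for protocol deviations gives a per-protocol estimate. That can be useful as a secondary view. Here it seems to be the only view of the primary endpoint, in a study meant to describe what happens in ordinary practice.

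The rule for leaving the set is also open. Nothing visible says what makes a deviation significant, who decides, when the set is fixed, or that the decision is taken without sight of the IPSS. With treatment known to all and a criterion that rests on investigator judgement, a man whose 12-month score is already recorded could be ruled ineligible and removed. If men removed in this way had done worse than those kept, the reported improvement would be too large. With no all-treated analysis beside it, a reader could not tell.

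**Working it through.** **1. Which set serves the primary endpoint?**

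| Section | What it settles |
|---|---|
| 8.4.1 | FAS not used for efficacy endpoints |
| 8.4.2 | EAS is the only other set defined |
| 8.5.2 | No set named |
| 8.5.3.1, 8.5.3.6 | EAS for IPSS over time and SHIM |
| 8.5.1.7 | FAS for secondary endpoints |
| 8.5.3.3 to 8.5.3.5, 8.5.3.7 | FAS for technical success, embolization, re-treatment, catheter removal |

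The EAS follows for the primary IPSS result by elimination. This is an inference, and it does not extend to every secondary endpoint.

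**2. Would an FAS analysis be enough?** Not reliably. The FAS consists of enrolled men, and section 15 counts as enrolled only men who meet every criterion. A man ruled ineligible after treatment could be argued out of the FAS as well.

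**3. Precision.** Inputs from 8.3: SD 8.5, two-sided 95% interval of full width 2, 10% missing.

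- Evaluable men needed: (1.96 x 8.5 / 1)^2 = 277.6, so 278. Allowing for missing data: 278 / 0.90 = 308.9, so 309.
- The plan states up to 500. The simple formula does not reproduce that figure. It is a ceiling and the stratum inputs are incomplete, so this does not show it to be wrong, and nothing below depends on it.
- With 500 enrolled and 10% missing, 450 remain. The simple half-width, without the finite-population term of 8.5.2, is 1.96 x 8.5 / sqrt(450) = 0.79.
- The target of +/- 1 is still met with 278 men, a loss of 1 - 278/500 = 44%. Interval width would therefore give no warning of selective removal.

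**4. Bias.** Let p be the share of men with an observed 12-month IPSS who are removed, and g the mean improvement in retained men minus that in removed men. The all-men mean is (1 - p) x retained + p x removed, so the retained mean overstates it by p x g. The documents give neither p nor g; every value here is an assumption.

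| p | g = 4 | g = 5 | g = 8.5 (1 SD) | g = 10 |
|---|---|---|---|---|
| 2% | 0.08 | 0.10 | 0.17 | 0.20 |
| 5% | 0.20 | 0.25 | 0.43 | 0.50 |
| 10% | 0.40 | 0.50 | 0.85 | 1.00 |

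A shift of 1 point needs p = 1/g: 20% at g = 5, 11.8% at g = 8.5, 10% at g = 10. A shift equal to the 0.79 half-width needs 0.785 / 8.5 = 9.2% at a 1-SD gap.

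**The case against.** Much of the case on the other side stands, and it limits the point.

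- **Missed or out-of-window visits.** A reader might infer that these count as significant deviations. The documents do not say so. The only example is eligibility failure. Section 7 has its own procedure for missed visits, and 8.5.1.2 analyses assessments by the visit entered in the eCRF.
- **Non-responders and the missing-data plan.** A reader might infer that the clause lets a non-responder be excluded and so undercuts the missing-data rules. Such a man has no 12-month IPSS. If kept, he would be given the age-specific average under 8.5.2.1, so excluding him hardly moves the mean. The bias formula applies only to men with an observed score.
- **Retroactive use of the follow-up criterion.** One exclusion reads "Patient is unable or unwilling to provide follow-up information". Applying it to a man who later stops responding is possible but not the natural reading: it is written as an entry criterion, and section 7 classes him as lost to follow-up.
- **Few true failures.** Entry criteria are broad, so the number removed may be small. The 1.0-point figure pairs the two largest values of the assumed range.
- **Population inferred.** Section 3.1 frames the primary objective around men eligible to complete a baseline IPSS and mentions no deviation exclusion.
- **No threshold.** The primary objective is estimation, with no stated success criterion, so no pass or fail decision turns on this.

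What remains unanswered is the open-ended clause, the absence of any lock on it, and the lack of an all-treated analysis of the primary endpoint.

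**Conclusion.** The point holds in limited form. Followed as written, and on the inference that 8.4.1 leaves the primary endpoint to the EAS, the plan yields a per-protocol estimate whose exclusions are undefined and can be decided with outcomes known. It permits such removal. A reader might go further and infer that removal will occur or that it must favour the device; the documents show neither, and the direction is only plausible.

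The size is illustrative. Assuming 5% to 10% of men with observed outcomes are removed and a gap of 5 to 10 points, the overstatement is 0.25 to 1.0 points against the +/- 1 target; at 2% and 4 points it is 0.08. This is worth amending because the better population costs little, not because a large bias has been shown. One part of the plan is redacted after 8.5.7.1, so the statements about what is absent refer to the visible text.

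**What to change.** 1. In 8.5.2, name the primary efficacy set: all men in whom PAE was performed or attempted and who were eligible to complete a baseline IPSS (as in 3.1), regardless of protocol deviations or later rulings on eligibility. Do not define it through the FAS, because of section 15. This wording also replaces the end-of-procedure catheter condition with a baseline one, which the sponsor should adopt knowingly.
2. Keep the deviation-free set as a sensitivity analysis. Limit its exclusions to facts documented before the PAE, fix them before the 12-month IPSS is reviewed, and report each with its reason.
3. Reconcile 8.4.1, 8.4.2, 8.5.1.7, 8.5.2, 8.5.3.1, 8.5.3.6 and 15 on which set serves which endpoint.

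The cost is wording in these sections and one extra table. The estimate may be slightly less favourable.
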